### ***6.6.3 Interim Analyses and Data Monitoring***

No interim analysis was planned.

### ***6.6.4 Multicenter Studies***

This is a multi-center study, which was conducted in the Depression Research Clinic at Stanford University, Tri-Service General Hospital, Taipei Veterans General Hospital, Linkou Chang Gung Memorial Hospital, Taipei City Hospital, Songde Branch, and Wanfang Hospital. All results will be listed by center.

### ***6.6.5 Multiple Comparisons / Multiplicity***

The Holm procedure will be carried out for the post-hoc test of the primary endpoint.

### ***6.6.6 Use of An “Efficacy Subset” of Subjects***

All analyzed populations were defined in section 5.3.1; no other population will be utilized in statistical analyses.

### **6.6.7 Active-Control Studies Intended to Show Equivalence**

Not applicable

### **6.6.8 Examination of Subgroups**

No subgroup analysis was conducted in the study. All center data will be pooled together for analyses of efficacy endpoint.

### **6.6.10 Random effect and fixed effect when modeling**

Not applicable

### **6.6.11 Outliers**

Outliers will not be excluded for and some extreme values will be excluded from this study.

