8.3 Analysis of Efficacy and Safety

The efficacy measures are conducted on the per-protocol (PP) and intent-to-treat (ITT) basis. The per protocol will be defined as (1) The drug compliance is at least 80% (2) Subjects have completed data to determine the primary endpoint. (3) Subjects cannot have protocol deviation. The protocol deviation will be defined as (1) Inclusion or exclusion criteria not satisfied. (2) Not permitted concomitant medications (3) Wrong randomized treatment prescribed. An intent-to-treat (ITT) basis will be defined as the data are analyzed by the treatment groups to which the randomized patients who take at least one dose of study medication and have any post-baseline safety data collected. The safety measures are conducted on the ITT basis. The data are analyzed utilizing the last observation carried forward (LOCF) technique to impute the missing data.

The efficacy and safety information recorded on CRF will be summarized by tables presented in frequency and percentage for categorical variables, in mean with SD as well as median with the minimum and maximum for continuous variables. The comparison between three groups will be analyzed by nonparametric method as appropriate. All adverse events will be summarized with coding term, severity, relationship to study drug by frequency tables with the counts and percentage. In addition, serious adverse events will be listed with event narration.

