## 5.3 Statistical Methods Planned in the Protocol and Determination of Sample Size

### 5.3.1 Populations for analysis

The efficacy measures are conducted on the per-protocol (PP) and intent-to-treat (ITT) basis. The per protocol will be defined as (1) The drug compliance is at least 80% (2) Subjects have completed data to determine the primary endpoint. (3) Subjects cannot have protocol deviation. The protocol deviation will be defined as (1) Inclusion or exclusion criteria not satisfied. (2) Not permitted concomitant medications (3) Wrong randomized treatment prescribed. An intent-to-treat (ITT) basis will be defined as the data are analyzed by the treatment groups to which the randomized patients who take at least one dose of study medication and have any post-baseline safety data collected.

The safety measures are conducted on the ITT basis.

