#### **5.4 Changes in the Conduct of the Study or Planned Analyses**

All the statistical analysis will follow protocolized statistical contents.

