### 6.1 Data Sets Analyzed

Two study populations are intention-to-treat (ITT) population and per-protocol (PP) populations which are defined in section 5.3.1.

The efficacy evaluations will be performed on both of the ITT and PP datasets while the safety evaluations will be performed on the ITT dataset. The primary conclusion will be made for the primary endpoint on the ITT population

Demographic and baseline (Visit 2) characteristics will be performed on the ITT population.

Sample size, mean, 95% confidence interval of mean, median, standard deviation, inter-quartile range, maximum and minimum will be summarized for continuous variables. For categorical variables, the frequency and percentage will be provided.

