### 6.4.1 Primary Efficacy Endpoint

In part II study, the primary endpoint is the net change of the MADRS total score at the 6th week after treatment (Mean MADRS total score at week 6 – Mean MADRS total score at baseline [Visit 2]).

Kruskal-Wallis test will be implemented to test the group difference.

The primary hypothesis will be:

$$\begin{aligned}
 H_0: & \text{The mean ranks of the groups are the same} \\
 H_a: & \text{The mean ranks of the groups are not the same}
 \end{aligned}$$

One a significant treatment effect is found, Wilcoxon rank sum test with Holm procedure will then be performed for comparisons between two treatment groups and the placebo group. The treatment group will be declared superior if null hypothesis is rejected and  $\mu_{t1}$  and/or  $\mu_{t2}$  is greater than  $\mu_p$ .

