### ***6.6.2 Handling of Dropouts or Missing Data***

Missing data caused by premature termination will be utilized the last observation carried forward (LOCF). However, the LOCF method will only be applied to data on efficacy. No imputation will be done for safety data.

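### SAP 6.6.11 both forbids and orders the exclusion of extreme values, so the data entering the primary test are not fixed

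*SAP*

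**What the plan says.** The whole of SAP 6.6.11 is: "Outliers will not be excluded for and some extreme values will be excluded from this study". The amendment table in SAP 11.5 does not touch this section, so it is current text.

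The rest of the primary analysis is specified. The endpoint is the change in MADRS total score from baseline to week 6, and SAP 6.4.1 states: "Kruskal-Wallis test will be implemented to test the group difference". Wilcoxon rank sum tests of each dose against placebo follow, with the Holm procedure. On the analysis set, SAP 6.1 says: "The primary conclusion will be made for the primary endpoint on the ITT population".

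Two general statements bear on the question indirectly. SAP 5.4 says: "All the statistical analysis will follow protocolized statistical contents". SAP 6.6.6 adds that "no other population will be utilized in statistical analyses".

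On missing data, SAP 6.6.2 limits LOCF to efficacy data missing because of premature termination. Protocol 8.3 has no such limit: "The data are analyzed utilizing the last observation carried forward (LOCF) technique to impute the missing data".

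**The concern.** A pre-specified analysis should determine its own input data. Here two competent analysts can follow the same sentence, run the primary test on different sets of week-6 scores, and under some rules reach different conclusions. Afterwards nobody could check whether a given removal complied with the SAP.

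There is a second, dependent gap. If a completer's week-6 score is removed, the SAP does not say whether the patient drops out of the test or is given an earlier value. Under SAP 6.6.2 LOCF would not apply, because the patient did not terminate early. Under Protocol 8.3 it could.

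The sentence covers the whole study, so it also reaches safety. The effect there is limited to the numeric laboratory and vital-sign summaries (SAP 6.5.3 and 6.5.5).

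**Working it through.** **Does any other text settle it?**

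- Protocol section 8 is silent on outliers, so the deferral to the protocol in SAP 5.4 leads to no rule.
- SAP 5.3.1, 6.1 and 6.6.6 fix which patients are analysed, not which of their observed values.
- SAP 6.4.1 names the test and says nothing about exclusions.
- SAP 6.6.2 concerns missing data, not data deliberately removed.

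These passages favour keeping all values, but none addresses the point. The sentence can also be read as two grades, with outliers kept and only more distant values removed. That reading still gives no cut-off.

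**How much could it matter?** The documents give no figure to reproduce: the 60 patients in Part II are stated without an effect size, SD or power. The simulation therefore uses these inputs.

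- From the documents: 60 / 3 = 20 per arm; Kruskal-Wallis at two-sided 0.05, then Wilcoxon against placebo with Holm.
- Assumed: change score with mean −12 and SD 9, rounded to integers; either normal or t(3) scaled to SD 9; removed values dropped. Favourable means a larger fall in MADRS.
- Assumed exclusion rules: 2, 2.5 or 3 SD from the mean, or 1.5×IQR or 3×IQR beyond the quartiles, computed either on pooled data or within each arm.

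Type I error comes from 20,000 null trials per distribution. The Monte Carlo standard error is √(0.05 × 0.95 / 20,000) = 0.0015. The last column is the share of trials in which the Kruskal-Wallis decision differs from the analysis with no exclusion when both doses are 5 points better (assumed; 10,000 normal and 8,000 t(3) trials).

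| Rule | Type I error, normal / t(3) | Decision differs, normal / t(3) |
|---|---|---|
| No exclusion | 4.95% / 4.78% | – |
| Pooled 3×IQR | 4.95% / 4.83% | 0.0% / 4.2% |
| Pooled 3 SD | 4.93% / 4.81% | 0.6% / 6.6% |
| Pooled 2.5 SD | 4.88% / 4.76% | 4.0% / 9.5% |
| Pooled 1.5×IQR | 4.86% / 4.84% | 3.8% / 12.3% |
| Pooled 2 SD | 4.63% / 4.81% | 11.7% / 12.8% |
| Per-arm 3 SD | 5.05% / 5.19% | 0.3% / 5.0% |
| Per-arm 3×IQR | 5.15% / 5.64% | 0.5% / 6.4% |
| Per-arm 2.5 SD | 5.95% / 6.05% | 3.3% / 9.4% |
| Per-arm 1.5×IQR | 8.14% / 8.89% | 7.4% / 13.8% |
| Per-arm 2 SD | 9.74% / 8.01% | 11.7% / 13.4% |

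- **False declaration that at least one dose is better:** 1.69% / 1.65% with no exclusion, 1.7–2.0% with per-arm 3 SD or 3×IQR, and 2.9–3.3% with per-arm 2 SD or 1.5×IQR.
- **Values removed:** on average out of 60, per-arm 3 SD removes 0.03 / 0.66 and per-arm 2 SD removes 2.18 / 3.31.
- **Power (normal data, 5-point effect):** 37.7% with no exclusion and 30.5% with pooled 2 SD. A pooled rule can therefore change the result without inflating error.
- **Sensitivity to the SD:** with SD 7 and 11 (normal, 10,000 trials each), no exclusion gives 4.8–5.0%, pooled rules 4.8–5.3%, per-arm 3 SD 5.0–5.1%, per-arm 1.5×IQR 8.3–8.6% and per-arm 2 SD 10.0–10.2%.

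A separate set of 10,000 null trials per distribution gave the same picture: 5.3% / 4.6% with all values kept, 5.4% / 5.7% with per-arm 3×IQR and 8.3% / 9.3% with per-arm 1.5×IQR.

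**The case against.** The strongest reply is that the sentence begins by keeping outliers, so its only coherent exclusion reading is a strict one. The 2 SD, 2.5 SD and 1.5×IQR rules would discard ordinary outliers and contradict the first clause. The sentence also does not mention arms. For the strict rules (3 SD, 3×IQR) type I error stays at 4.8–5.6%, and with normal data the decision changes in at most 0.6% of trials. The test is rank-based, which limits the leverage of any one value.

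The heavy-tailed figures are also on the high side, because the simulated changes are unbounded while MADRS runs from 0 to 60 (ten items scored 0–6, Protocol 6.2). With an assumed baseline of mean 30 and SD 5, bounding the scores brings the strict rules to 4.8–5.4% type I error. Changed decisions fall to 3.3–5.9%, against 4.5–6.5% unbounded in the same run; with bounded normal data they are at most 0.9%.

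Finally, the general passages lean towards no exclusion, and the garbled wording suggests a slip.

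Most of this stands as a limit on size. The looser and per-arm figures show a range over assumed rules, not a reading of the text. It does not remove the defect. The strict reading still requires removal of unspecified values, nothing in the SAP confines removal to a strict threshold, and a lost word could reverse the meaning either way. The LOCF gap arises only if a value is removed, and its effect has not been quantified.

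**Conclusion.** The concern holds: the section is wrong as written, and it must be corrected because it leaves the input to the primary test undetermined. That conclusion rests on the contradictory wording; the simulation only bounds the consequence.

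The consequence ranges from negligible (a strict rule with near-normal data) to roughly a doubling of type I error (loose per-arm rules). Rules fixed in advance on pooled data do not inflate error, but they can still change the decision or reduce power. The figures assume an SD of 9, normal or t(3) changes, a 5-point benefit where an effect is simulated, and removed values being dropped. Choosing among rules or values with arm labels known would inflate error further. The text does not describe such conduct, but it does not rule it out.

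**What to change.** Replace SAP 6.6.11 with wording such as:

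> No observed value is excluded from the primary or secondary ITT efficacy analyses or from the safety summaries because it is extreme. Implausible values are queried and corrected at source before database lock and unblinding. Any additional analysis omitting extreme values is a sensitivity analysis only, using a numerical threshold computed on data pooled across arms and fixed before unblinding. The per-protocol exclusions in section 5.3.1 are unaffected.

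The first sentence alone resolves the contradiction and makes the LOCF question moot for extreme values. The others close off discretionary removal. Excluding values would bring little benefit anyway for a rank test on a bounded scale.

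The cost is replacement text for one SAP section. Design, data collection, analysis sets and sample size do not change.

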### **6.6.12 Calibration of Laboratory Data Between Centers**

Units of continuous laboratory data will be unified; the ones used in a plurality of center will be the standard.

## 7. DOCUMENTATION OF STATISTICAL METHODS

### 7.1 Documentation of Statistical Methods

Following SAS procedures will be applied for statistical methods mentioned in Chapter 6.

SAS procedure	Statistical Analysis Method	Comment
Freq	Frequency table	
	Cochran-Mantel-Haenszel Test	Test of association between variables by controlling for multiple centers
Sgplot	Graph	
NPAR1WAY	Kruskal-Wallis test	To test group difference of continuous variables
	Wilcoxon rank sum test	Post-hoc test
MULTTEST	Holm's Procedure	Significant level control for Multiplicity
MEANS	Descriptive Statistics	Means, SD, Min, Max, Med, IQR, P1, P3

\*Center effect will be incorporated in only when degree of freedom is sufficient.

## **8. DATA HANDLING PROCEDURE**

### **8.1 Coding System**

The MedDRA system (version 20.0) is used to code adverse events.

Concomitant medication will be coded via WHODRUG.

General medical history term will be coded via ICD-10 coding system

### **8.2 Data Storage and Analysis**

All data are stored in the VCROCTIS system.

Statistical evaluation will be performed using SAS 9.4 (SAS-Institute Inc., Cary, NC).

## **9. STUDY SUBJECTS**

### **9.1 Disposition of Subjects**

The number and percentage of randomized subject no. and analysis population will be tabulated by center and treatment.

### **9.2 Withdrawal of Subjects**

Frequency table of the reasons for subject withdraw from study will be presented by center and treatment.

### **9.3 Protocol Deviations**

Protocol deviations will be listed and will be tabulated by center and treatment.

## 11. APPENDICES

### 11.1 Normal Ranges For Laboratory Variables

Will be listed in data listings

### 11.2 Table of Contents (TOC) for Tables, Figures and Listing

Refer to section 14 and 16.2 in clinical study report

No further SAP amendment will be required for the deviation of TOC when the changes are still complied with the main text SAP.

### 11.3 Mock-up tables

Refer to attachment “MUT\_BOLPDCA20141117\_20180626\_01\_final\_20190611.pdf”

### 11.4 Version Control Information of SAP

Document	Version	Approved date
Final	20180626_00	Apr-19-2019
Final	20180626_01	June-14-2019

## 11.5 Contents of Amendment of SAP

Page	Before version : 00	Page	Content after modification Version : 01
20~ 21	
6.4 Analysis of Efficacy
 
Results of efficacy will be presented with descriptive statistics (i.e. sample size, number of missing data, mean, 95% confidence interval of mean, median, standard deviation, inter-quartile range, maximum and minimum) for continuous parameters by part, visit, and treatment.
	20~ 21	
6.4 Analysis of Efficacy
 
Results of efficacy will be presented with descriptive statistics (i.e. sample size, number of missing data, mean, 95% confidence interval of mean, median, standard deviation, inter-quartile range, maximum and minimum) for continuous parameters by part, visit, and treatment. Line charts of all efficacy outcomes will be generated and presented as mean and standard deviation.

22	
Definition of partial responder
 
...partial responder are defined as participants with at least 25% and no more than 50% decrease in total score from baseline) and the 95% confidence interval (CI) will be computed.
	22	
Definition of partial responder
 
...partial responders are defined as participants with at least 25% and no more than 50% decrease in total score from baseline).

22	
6.5.1 Adverse events (AEs)
 
For TEAE, incidence tables of severity, action taken, relationship to study drug, outcome and serious AE or not will be presented by part, center, preferred term and treatment.
	22	
6.5.1 Adverse events (AEs)
 
For TEAE, incidence tables of severity, action taken, relationship to study drug, outcome and serious AE or not will be presented by part, center, preferred term and treatment.
 
The frequency distribution of severity, action taken, relationship to study drug, and outcome of all AE events will be presented by part, center, and treatment.

23	
6.5.4 Physical Examination (PE)
 
Only when abnormality is recorded, the corresponding body system will be analyzed and reported using a transition table. The type of transition includes normal -> normal, normal -> abnormal, abnormal -> abnormal, and abnormal-> normal for each body system from baseline (Visit 2).
	23	
6.5.4 Physical Examination (PE)
 
The corresponding body system will be analyzed and reported using a transition table. The type of transition includes no change, change to normal, change to non-clinical significance, (NCS), change to clinical significance (CS) for each body system from baseline (Visit 2).

23	
6.5.5 Vital Signs
 
Descriptive statistics of net changes in vital signs including systolic and diastolic blood pressure, heart rate and
	23	
6.5.5 Vital Signs
 
Descriptive statistics of net changes in vital signs including systolic and diastolic blood pressure, heart rate and

	body temperature will be presented by part, center, visit, and treatment.		body temperature will be presented by part, center, visit, and treatment. Results of clinical significance with regard to vital sign will be summarized with frequency and percentage.
23	
6.5.6 ECG
 
Frequency table and change in ECG result will be summarized by part, center, visit and treatment. The transition of ECG is define as following 4 groups: normal -> normal, normal -> abnormal, abnormal -> abnormal, and abnormal-> normal.
	23	
6.5.6 ECG
 
Frequency table and change in ECG result will be summarized by part, center, visit and treatment. The transition of ECG is define as following 4 groups: no change, change to normal, change to non-clinical significance, (NCS), change to clinical significance (CS).

30	
11.3 Mock-up tables
 
Refer to attachment  “MUT_BOLPDCA20141117_20180626_00_final20190411.pdf”
	30	
11.3 Mock-up tables
 
Refer to attachment  “MUT_BOLPDCA20141117_20180626_01_final_20190611.pdf”

